Real-world outcomes for patients with A/MBC who were treated with palbociclib in combination with AI or fulvestrant have been reported in several publications and at medical congresses. A comparative analysis of palbociclib + letrozole vs. letrozole alone was presented at the European Society for Medical Oncology (ESMO) 2019 congress.⁹ Using the Flatiron Health Analytics Database consisting of U.S. community physicians, a total of 1,416 electronic health records of patients with HR+/HER2- MBC were reviewed to assess the comparative effectiveness of palbociclib + letrozole (n=798) compared to letrozole alone (n=618). Results showed that patients who took palbociclib + letrozole had a median progression-free survival (PFS) of 24.5 months while patients on letrozole alone had a median PFS of 17.1 months (HR=0.68, 95% CI: 0.56-0.84). OS was also favorable for patients taking palbociclib + letrozole compared to patients taking letrozole alone (HR=0.57, 95% CI: 0.41-0.79). Another study reported on the Ibrance Real World Insights

Study (IRIS) involving medical chart review of 652 U.S. patients with A/MBC treated with palbociclib in combination with either AI (n=360) or fulvestrant (n=292).¹⁰ The 12-month progression-free rate was 84.1% for patients treated with palbociclib + AI and 79.8% for those treated with palbociclib + fulvestrant. The 12-month survival rates were 95.1% for palbociclib + AI and 87.9% for palbociclib + fulvestrant.

This present study is designed to examine further real-world evidence on the use of palbociclib, ribociclib, and abemaciclib in both male and female patients with A/MBC. This study is designed to describe patient characteristics, treatment patterns, and clinical effectiveness outcomes in a cohort of patients diagnosed with HR+/HER2- A/MBC who were treated with any CDK4/6i combination therapies with AI in the U.S. community oncology setting.

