9.3.4. Derived Variables

Variables suggested to be derived for this study's purpose will be generated by Pfizer analytical team. Final algorithm to derive the variables will be further determined by Pfizer. The suggested variables derived from abstracted and extracted data will include the following:

1. Age at index date, at initiation of the earliest endocrine-based regimen, and at first treatment regimen after the index date.
2. Weighted index of comorbid disease condition. Weighting of comorbid conditions (not including breast cancer) will follow the weighting as specified in the Charlson Comorbidity Index.
3. Start and end dates of anti-cancer treatments from the index date through the end of the record or the end of the study, whichever occurs first.
4. Treatment regimens, derived from oral and infused agents delivered, including start and end dates.
5. Endocrine sensitivity prior to the index date, defined as endocrine sensitive vs. resistant vs. refractory based on adjuvant endocrine therapy experience. Endocrine sensitive: ≥24 months without recurrence/progression after completion of endocrine therapy in the adjuvant setting; Endocrine resistant: recurrence/progression after completion of endocrine therapy, and within 24 months of completion of endocrine therapy; Endocrine refractory: recurrence/progression while on endocrine therapy in the adjuvant setting, defined as occurring while on or within <30 days after discontinuation of endocrine therapy. The 30 day window allows that endocrine therapy may be discontinued because of a perceived progression before that progression is actually documented.
6. Primary endocrine resistance defined as a relapse while on the first 2 years of adjuvant endocrine therapy or disease progression within the first 6 months of first-line endocrine therapy for A/MBC, while on endocrine therapy.

PFIZER CONFIDENTIAL

7. Secondary (acquired) endocrine resistance defined as a relapse while on adjuvant endocrine therapy but after the first 2 years or a relapse within 12 months of completing adjuvant endocrine therapy, or disease progression ≥ 6 months after initiating endocrine therapy for A/MBC, while on endocrine therapy.

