4.1.1. Inclusion criteria

Patients must meet all of the following inclusion criteria to be eligible for inclusion in the study:

1. *Female or male sex.*
2. *Diagnosis (confirmed by clinical review) of A/MBC, defined as breast cancer at stage IIIB, stage IIIC, stage IV or identified as having distant metastasis.*
3. *Age ≥ 18 years at A/MBC diagnosis.*
4. *Initiated a CDK4/6i in combination with an AI as initial endocrine-based therapy after A/MBC diagnosis on or after 2/3/2015 and before 4/1/2019.*
 - *Note that the date of the start of the inclusion period reflects the month that the first CDK4/6i (ie, Palbociclib) received U.S. FDA approval.*
5. *Evidence of ER or PR positive disease, or absence of any indication of ER and PR negative disease closest to A/MBC diagnosis (ie, patients are eligible without affirmative indication of ER/PR+ status as long as ER/PR- indication is not present).*
6. *Evidence of HER2 negative disease, or absence of any indication of HER2 positive disease closest to A/MBC diagnosis (ie, patients are eligible without affirmative indication of HER2- status as long as HER2+ indication is not present).*

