4.2. Subgroups

Summaries of study outcomes may be repeated focusing alternatively on but not limited to the following subgroups of interest—sample size permitting—which will be defined on the basis of:

- Age (years): ≤ 50 , 51-64, 65-74, ≥ 75 ;
- Gender, if number of males is low then we can restrict results to females;
- Race: White, Black, Other;
- Disease stage at initial diagnosis: I or II, III, IV;
- ECOG performance status: 0, 1 or 2, ≥ 3 ;
- Site of metastasis: Visceral, Non-visceral, Bone only;
- Number of metastatic sites: 1, 2, ≥ 3 ;

PFIZER CONFIDENTIAL

- Menopausal status: premenopausal, perimenopausal, Postmenopausal, undocumented;
- Hormone therapy prior to A/MBC diagnosis: yes, no;
- Chemotherapy prior to A/MBC diagnosis: yes, no;
- Surgery prior to A/MBC diagnosis: yes, no;
- Radiation therapy prior to A/MBC diagnosis: yes, no;
- Disease free interval: ≤ 12 months, > 12 months;
- Starting dose: by starting dose levels for Palbociclib, CCI

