5.1. DEMOGRAPHIC AND CLINICAL CHARACTERISTICS

Variable	Operational definition
Demographic characteristics	
Age	Age at A/MBC diagnosis, years
Age category	≤ 50 , 51-64, 65 –74, ≥ 75 years
Sex	Female or Male
Race	White, Black, Asian, Other, Unknown
Region of residence	Based on state where the patient resides: Northeast, Midwest, South, West
Insurance status	Private only, public only, public and private, or neither reported at index date and reported at initiation of the earliest endocrine-based therapy after the index date.
Clinical characteristics	
Menopausal status	(Pre, Peri, Post, UD) nearest in time to the date of, but before, index date.
Type of MBC	De novo MBC (newly diagnosed): Stage 4 at initial BC diagnosis Recurrent MBC: Stages 0-3 at initial BC diagnosis
Modalities of treatment received at any point prior to A/MBC diagnosis	Surgery (yes/no), Radiation (yes/no), Chemotherapy (yes/no), Hormone therapy (yes/no)

PFIZER CONFIDENTIAL

ECOG performance score	ECOG performance at index date (\pm 60 days), 0, 1,2,3,4,5, or missing. Where available, Karnofsky performance status will be converted to the corresponding ECOG score.
Disease stage at initial BC diagnosis	Stage I, II, III, IV, unknown/ undocumented
Disease stage at index date (date of A/MBC diagnosis)	IIIB, IIIC, or IV
Time from initial BC diagnosis to first MBC diagnosis	Months from the date of initial BC diagnosis to the date of metastatic diagnosis.
Disease free interval	The number of months between completion of adjuvant therapy and diagnosis of A/MBC.
Sites of distant metastasis at index date	Bone; Chest Wall; Contralateral Breast; Distant Lymph node(s); Liver; Lung; Peritoneum; Pleural nodules; Malignant pleural effusion; Skin; Brain; Undocumented; Other Specified. All sites will be reported as (yes/no).
Visceral metastasis at index date	Metastasis at one or more of the following sites: liver, pancreas, intestines, lung, heart, malignant pleural effusion, peritoneum, pleura. Other metastasis sites, including bone or non-visceral metastasis, may be present.
Non-visceral metastasis at index date	Metastasis at one or more of the following sites: bone, brain, skin, chest wall, contralateral breast, or distant lymph nodes.
Bone-only metastasis at index date	Bone metastasis, with no metastasis at any other identified site

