Disease histology nearest in time to index date	Adenoid cystic; Cribriform; Ductal; Inflammatory; Intraductal; Lobular; Medullary with lymphoid stroma; Medullary, NOS; Mucinous; Paget's disease and infiltrating; Paget's disease and intraductal; Papillary; Secretory; Squamous cell; Tubular; Undifferentiated; Undocumented, Other, specify.

PFIZER CONFIDENTIAL

Endocrine sensitivity	
Sensitive/Resistant/Refractory
 
Endocrine sensitive vs. resistant vs. refractory based on adjuvant endocrine therapy experience. Endocrine sensitive: ≥ 24 months without recurrence / progression after completion of endocrine therapy in the adjuvant setting; Endocrine resistant: recurrence / progression after completion of endocrine therapy, and within 24 months of completion of endocrine therapy; Endocrine refractory: recurrence / progression while on endocrine therapy in the adjuvant setting, defined as occurring while on or within < 30 days after discontinuation of endocrine therapy. The 30 day window allows that endocrine therapy may be discontinued because of a perceived progression before that progression is actually documented.

Type of endocrine resistance	
Primary/Secondary
 
Primary endocrine resistance defined as a relapse while on the first 2 years of adjuvant endocrine therapy or disease progression within the first 6 months of first-line endocrine therapy for A/MBC, while on endocrine therapy.
 
Secondary (acquired) endocrine resistance defined as a relapse while on adjuvant endocrine therapy but after the first 2 years or a relapse within 12 months of completing adjuvant endocrine therapy, or disease progression ≥ 6 months after initiating endocrine therapy for A/MBC, while on endocrine therapy.

Comorbidities present at index date	
Myocardial infarction, congestive heart failure, peripheral vascular disease, cerebrovascular accident, hemiplegia, chronic obstructive pulmonary disease, ulcer disease, diabetes, renal disease, connective tissue disease such as rheumatoid arthritis or lupus, Alzheimer's or other dementia, cirrhosis or other serious liver disease, leukemia, lymphoma, metastatic solid tumor (other than breast cancer), and HIV/AIDS, hypertension and hyperlipidemia.
 
Indicated as present or not indicated as present at index date.

PFIZER CONFIDENTIAL

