First Quartile/Third Quartile	
Median/IQR	

PFIZER CONFIDENTIAL

Disease Histology, n (%) Adenoid Cystic Cribriform Ductal Inflammatory Intraductal Lobular Medullary with Lymphoid Stroma Medullary, NOS Mucinous Paget's Disease and Infiltrating Paget's Disease and Intraductal Papillary Secretory Squamous Cell Tubular Undifferentiated Undocumented Other, specify	
ECOG Performance Score ^b , n (%) 0 - Normal activity 1 - Symptoms demonstrated, but the patient remains ambulatory, and able to perform self-care 2 - Ambulatory >50% of the time and requires occasional assistance 3 - Ambulatory <50% of the time and requires nursing care 4 - Bedridden 5 - Death Missing	
Comorbidities, n (%) Myocardial infarction Congestive heart failure Peripheral vascular disease Cerebrovascular accident Hemiplegia Chronic obstructive pulmonary disease Ulcer disease Diabetes Renal disease Connective tissue disease Alzheimer's or other dementia Cirrhosis or other serious liver disease Leukemia Lymphoma	

PFIZER CONFIDENTIAL

Metastatic solid tumor (other than breast cancer) HIV/AIDS Hypertension Hyperlipidemia	
Modified Charlson Comorbidity Index ^c Mean/SD N/Missing Values Min/Max First Quartile/Third Quartile Median/IQR	
Sites of distant metastasis, n (%) Bone Chest wall Contralateral breast Distant lymph node(s) Liver Lung Peritoneum Pleural nodules Malignant pleural effusion Skin Brain Undocumented Other, specify	
Number of Metastatic Sites Mean/SD N/Missing Values Min/Max First Quartile/Third Quartile Median/IQR	
Visceral Metastasis ^d Yes No Missing	
Non-visceral Metastasis ^e Yes No Missing	
Bone-only Metastasis ^f Yes No Missing	
Modalities of Treatment, n (%) Surgery Radiation	

PFIZER CONFIDENTIAL

Chemotherapy	
Hormone therapy	
Missing	
Disease Free Interval (months)	
Mean/SD	
N/Missing Values	
Min/Max	
First Quartile/Third Quartile	
Median/IQR	
Endocrine Sensitivity, n (%)	
Sensitive	
Resistant	
Refractory	
Missing	
Endocrine Resistance, n (%)	
Primary	
Secondary	
Missing	

^a Percentage is based on the number of female patients.

^b Karnofsky performance status is converted to corresponding ECOG score

^c Weighting of comorbid conditions (not including breast cancer) will follow the weighting as specified in the Charlson Comorbidity Index.

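### The endocrine-resistance row in Table 2 is partly set by progression on the study therapy; the site subgroups and the Type of MBC label also need redefining

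*SAP*

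**What the plan says.** **Endocrine resistance.** SAP 5.1, repeating Protocol 9.3.4 items 6 and 7, gives each class an adjuvant limb and an on-treatment limb. Primary means relapse on adjuvant treatment before 2 years have passed; to this the definition adds "or disease progression within the first 6 months of first-line endocrine therapy for A/MBC, while on endocrine therapy". Secondary means later adjuvant relapse, relapse within 12 months of completing adjuvant therapy, or progression at 6 or more "months after initiating endocrine therapy for A/MBC, while on endocrine therapy". The result is reported in SAP Appendix 1, Tables 2a and 2b, as "Endocrine Resistance, n" (%), with the levels Primary, Secondary and Missing.

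Inclusion criterion 4 (SAP 4.1.1) requires that the patient "Initiated a CDK4/6i in combination with an AI as initial endocrine-based therapy after A/MBC diagnosis". Protocol 9.3.1 defines first line as the line containing that therapy. The index date is the date of A/MBC diagnosis (SAP 5).

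The neighbouring variable is anchored differently in Protocol 9.3.4 item 5: "Endocrine sensitivity prior to the index date, defined as endocrine sensitive vs. resistant vs. refractory based on adjuvant endocrine therapy experience".

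**Site subgroups.** SAP 4.2 lists, as one optional subgroup variable, "Site of metastasis: Visceral, Non-visceral, Bone only". SAP 5.1 defines Non-visceral as "Metastasis at one or more of the following sites: bone, brain, skin, chest wall, contralateral breast, or distant lymph nodes".

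**Type of MBC.** SAP 5.1 has two levels: de novo (stage 4 at initial diagnosis) and recurrent (stages 0 to 3 at initial diagnosis). Stage IIIB or IIIC is by itself enough for eligibility (SAP 4.1.1, criterion 2), and Protocol 9.3.2 items 8 and 9 expect patients at that stage at index.

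**The concern.** A patient characteristic in this cohort should be fixed before the study therapy starts. Here, progression on the study therapy, which is also an rwPFS event (SAP 5.3), decides whether and how a patient is classed as resistant. The row therefore mixes history with outcome, and its percentages grow as follow-up lengthens. A reader would naturally take it as prior endocrine experience. If rwPFS were ever broken down by this variable, the comparison would be circular.

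The other two points are smaller. If the site subgroups are run, the Non-visceral rwPFS and OS results will include patients with visceral disease. In the Type of MBC row, some patients will be called recurrent who have had no recurrence.

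**Working it through.** **1. Endocrine resistance: reading the definitions together**

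- Criterion 4 and Protocol 9.3.1 make the initial, first-line endocrine therapy for A/MBC the study CDK4/6i + AI. Both on-treatment limbs therefore use events after index.
- A patient with no adjuvant endocrine therapy can be classified only by progressing after index.
- The classes are not exclusive. Relapse in year 1 of adjuvant therapy plus progression at month 14 on study therapy meets both. The secondary limb is not restricted to first line, so progression at month 4 and again on a later endocrine therapy can also meet both. No precedence rule is given.
- A patient who meets neither definition has no level in the Table 2a shell except Missing.

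**2. How many patients the on-treatment limbs could reach**

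The plan states no figure to reproduce, so this is an illustration.

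Inputs from the documents:
- Therapy starts from 2/3/2015 to before 4/1/2019.
- 1100 to 1300 patients.
- Two cited results in Protocol 7: median PFS of 24.5 months with palbociclib + letrozole, and "The 12-month progression-free rate was 84.1% for patients treated with palbociclib + AI".

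Assumptions:
- Exponential PFS and uniform start dates.
- Everyone is observed to 12/1/2019, the date Protocol 9.5 assumes for the start of data collection. Follow-up then runs from 8.02 to 57.89 months.

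Formulas, with u the follow-up time:
- Share with an event by cutoff = mean of 1 − exp(−λu) over u from 8.02 to 57.89.
- Share with an event before 6 months = 1 − exp(−6λ).

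| | From 84.1% at 12 months | From 24.5-month median |
|---|---|---|
| λ per month | −ln(0.841)/12 = 0.01443 | ln 2/24.5 = 0.02829 |
| Event before 6 months | 8.3% | 15.6% |
| Event at 6 months or later | 28.2% | 41.7% |
| Any event by cutoff | 36.5% | 57.3% |
| Patients, of 1100 to 1300 | 401 to 474 | 630 to 745 |
| Any event, cutoff 12 months later | 46.6% | 69.6% |
| Added by the later cutoff | +10.1 points | +12.3 points |

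All of the added events fall in the 6-months-or-later group, although nobody's pre-index history has changed.

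These shares are upper bounds on those meeting the on-treatment limbs, because PFS events include deaths and progression off endocrine therapy. Some of these patients will also hold an adjuvant label.

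Allowance for deaths: the cited 12-month survival with palbociclib + AI is 95.1%. If the cited progression-free rate counts deaths as events, deaths without progression are at most (100 − 95.1)/(100 − 84.1) = 4.9/15.9 = 31% of 12-month events. Applying that share throughout leaves 0.365 × 0.69 = 25% to 0.573 × 0.69 = 40%.

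**3. Site subgroups**

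The Visceral definition allows other sites to be present, and the Non-visceral definition does not exclude visceral sites. A patient with liver and bone disease meets both, and every bone-only patient is also Non-visceral. Enumerating all 2047 non-empty patterns of 11 named sites (5 visceral, 6 non-visceral) gives 1953 that meet both definitions. These are pattern counts, not patient shares.

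The documents do not give the patient share. Let v be the proportion with visceral disease and b the proportion of those who also have a listed non-visceral site, and suppose every other patient has a listed non-visceral site. The visceral share of the Non-visceral group is then vb/(vb + 1 − v):
- v = 0.35, b = 0.4: 0.14/0.79 = 18%
- v = 0.55, b = 0.8: 0.44/0.89 = 49%

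Both pairs of inputs are assumed.

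**4. Type of MBC**

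Take a patient first diagnosed at stage IIIB with that diagnosis as index. She is eligible, is stage 3 at initial diagnosis, and is therefore labelled recurrent without having recurred. Table 2a covers All Eligible Patients and offers no other level except Missing. The number of such patients cannot be derived from the documents.

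**The case against.** The on-treatment limbs may be deliberate. Protocol 9.3.4 restricts endocrine sensitivity to the period before index but does not restrict resistance, and the SAP carries that wording over. Prior endocrine experience already has its own row. Table 2 is not titled baseline, and Objective 1a does not list endocrine resistance or Type of MBC among its characteristics. The study has no hypotheses and no covariates, and resistance is not a listed subgroup. The protocol also leaves the final derivation algorithm to the sponsor.

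These points limit the consequence, and that limit stands: no full-cohort effectiveness estimate changes. They do not rescue the row. The SAP is where the algorithm should be settled, and it repeats the mixed rule with no precedence and no level for patients who are not resistant. Even if the mixture was intended, the row cannot be programmed unambiguously, and it reports outcome events among patient characteristics.

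The size estimate is soft, as labelled. SAP 5 puts the cutoff at the end of curation, which would raise the shares; incomplete observation would lower them.

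On the smaller points, the subgroups are optional and not stated to be exclusive, and the separate Yes/No site rows in Table 2a are not miscounted. Type of MBC may be meant only for metastatic patients, but the SAP does not say so. Stage at initial diagnosis and at index remain visible in their own rows.

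**Conclusion.** The concern holds on all three points. Endocrine resistance as defined is not a pre-treatment characteristic. It is partly the rwPFS event, it depends on the cutoff, and its classes are neither exclusive nor exhaustive. At most 36% to 57% of patients would meet an on-treatment limb by 12/1/2019, or about 25% to 40% after the deaths allowance, given exponential PFS, uniform starts, full observation and the two cited results. The site overlap is certain from the definitions, but its size rests wholly on assumed inputs and it matters only if those subgroups are run. The Type of MBC fault affects one descriptive row, by an unknown number. The sponsor should correct these before programming, chiefly for the resistance row.

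**What to change.** - **Endocrine resistance:** restrict the Table 2 row to the adjuvant, pre-index limbs. Use the levels primary, secondary, not resistant, no prior adjuvant endocrine therapy, and undocumented. Report progression on study therapy only under outcomes.
- **Site subgroups (SAP 4.2):** use exclusive levels: any visceral site; bone only; other non-visceral (no visceral site and not bone only); no distant metastasis; undocumented.
- **Type of MBC:** add a level for newly diagnosed locally advanced disease, for patients whose initial diagnosis at IIIB/IIIC is itself the index diagnosis. Keep recurrent for those whose A/MBC followed an earlier diagnosis.

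The cost is SAP definition and shell edits. Adjuvant hormone dates, recurrence date, stage and sites are already curated (Protocol 9.3.2). Narrowing the resistance definition needs a short note of departure from Protocol 9.3.4; Protocol 9.7 allows the SAP to modify protocol plans. Free-text sites recorded under Other need review, because pancreas, intestines and heart count as visceral but are not listed site codes. The adjuvant-only row will overlap somewhat with endocrine sensitivity, but it uses different time boundaries (2 years on therapy and 12 months after it).

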5.2. TREATMENT PATTERN ENDPOINT(S)

Variable	Operational definition
Treatment Regimen Duration	Months from the start date to the end date of a treatment regimen. For ongoing regimen, the end date is the data cutoff date.
Treatment Sequence Duration	Months from the start date of the first treatment regimen to the end date of the last treatment regimen within the same line of therapy. For ongoing regimen, the end date is the data cutoff date. This will be calculated for up to 3 lines of therapy.
The following dosing information will be presented for palbociclib, CCI	
Start dose	Start dose level of palbociclib, CCI
End dose	End dose level of palbociclib, CCI
Duration of Treatment	Months from the start date to the end date of the treatment. For ongoing treatment, the end date is the data cutoff date.
Reason for Discontinuing Treatment	Cost; Disease Progression; Patient Refusal/Request; Toxicity, specify; Death, Other, specify, Undocumented
Time to Dose Discontinuation	Months from the start date to the discontinuation date of the treatment.
Type of Dose Adjustments	Dose Modification; Schedule Changes; Dose Delay; Hold; Discontinuation
Time to First Dose Adjustment	Months from the start date to the first adjustment date of the treatment.

PFIZER CONFIDENTIAL

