8. RESEARCH QUESTION AND OBJECTIVES

The objective of this study is to describe the patient characteristics, treatment patterns, and clinical effectiveness outcomes for patients with a diagnosis of HR+/HER2- A/MBC who received CDK4/6i combination therapy with AI as the initial endocrine-based therapy in the A/MBC setting.

Primary Objectives:

1. Among patients with HR+/HER2- A/MBC receiving CDK4/6i combination therapy with AI as initial endocrine-based therapy:
 - a. Describe demographic and clinical characteristics.
 - Demographic characteristics will include age, sex, race, insurance status, menopausal status, and region of residence at A/MBC diagnosis;
 - Clinical characteristics will include stage of initial diagnosis, histology, Eastern Cooperative Oncology Group (ECOG) performance status (where available, Karnofsky performance status will be converted to corresponding ECOG score) and comorbid disease burden, HER2 and Estrogen receptor (ER)/Progesterone receptor (PR) status, number and sites of distant metastasis at A/MBC diagnosis (if applicable); modalities of treatment received prior to A/MBC diagnosis (chemotherapy, hormone therapy, surgery, radiation therapy) and disease free interval (time between completion of adjuvant therapy and diagnosis of A/MBC).
 - b. Describe treatment patterns.
 - Distribution of regimens from the diagnosis of A/MBC through the end of the record;

- Sequence of regimens across lines, through the end of the record of systemic therapy;
- Description of the dosing employed with administration of palbociclib, ribociclib, and abemaciclib. Description of the dosing will include the starting dose, end dose, dose adjustment (dose increase and dose reduction), reasons for dose adjustment (dose modification, schedule changes, dose delay, hold, or discontinuation), discontinuation, reason, and time to dose adjustment (discontinuation).

2. Among patients receiving Palbociclib + AI as initial endocrine-based therapy, examine clinical effectiveness outcomes including:
 - a. Real-world progression-free survival (rwPFS) will be assessed for the first endocrine-based therapy.
 - b. Overall survival (OS) will be assessed from start of the first endocrine-based therapy.
 - c. Real-world tumor response (rwTR) will be assessed as best overall response for each regimen received within the first endocrine-based therapy.

CCI [REDACTED]

[REDACTED]

[REDACTED]

[REDACTED]

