5.3. Efficacy/Effectiveness Endpoint(s)

Variable	Operational definition
Real-world progression-free survival	
Time in months from the initial endocrine-based therapy to the first progression or censoring date will be calculated.
 
For the purpose of this study, lines of therapy will be defined as the following Progression-based lines, in which a disease progression must occur for a new regimen to be interpreted as a new line of therapy.
 
Event: Any death or disease progression. Disease progression is taken to have occurred when a pathology report or radiological scan indicates disease progression and/or there is a physician progress note consistent with that determination. If patients did not die or have disease progression, they were censored at their last visit date during the study period for patients with only one line of therapy.

Overall survival	
Time in months from the initial endocrine-based therapy to death due to any cause or censoring date will be calculated.
 
Event: Any death recorded in the data extract. Patients who did not die will be censored at the time of data cutoff (assuming this is the last date the SSDI is searched).

Real-world tumor response	
Real-world tumor response (rwTR) will be assessed as best overall response for each regimen received within the initial endocrine-based therapy.
 
Responses will be classified as Complete response (CR); Partial response (PR); Stable disease (SD); Progressive disease (PD); Not evaluable (NE); or Undocumented. The date of the first positive response (CR or PR) and of the best overall response for each regimen will be collected.

Response rate	
The number of patients with complete response or partial response divided by the number of patients with at least one tumor assessment while on the initial endocrine-based therapy.

PFIZER CONFIDENTIAL

Time to first positive response	Months from the start date of the initial endocrine based therapy to the date of the first positive response (CR or PR).
Duration of response	Month from the date of the first positive response (CR or PR) to the date of first PD assessment or death. Patients without a PD assessment or death are censored at the the data cutoff date.
Duration of initial endocrine-based treatment	Months from the start date of the initial endocrine-based therapy to the end date of the initial endocrine-based therapy.

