^d Visceral: metastasis at one or more of the following sites: liver, pancreas, intestines, lung, heart, malignant pleural effusion, peritoneum, pleura. Other metastasis sites, including bone or non-visceral metastasis, may be present.

^e Non-visceral: metastasis at one or more of the following sites: bone, brain, skin, chest wall, contralateral breast, or distant lymph nodes.

^f Bone only: Bone metastasis, with no metastasis at any other identified site.

Table 2b. Summary of Clinical Characteristics – Palbociclib + AI Patients

Repeat Table 2a for patients receiving Palbociclib with AI as initial endocrine-based therapy.

CCI

Table 3a. Summary of Treatment Regimen Duration – All Eligible Patients

		Treatment Regimen Duration (months)				
		n	%	Mean	SD	Median
Line 1	Regimenx	XXX	XXX	XXX	XXX	XXX
	Regimeny	XXX	XXX	XXX	XXX	XXX
	Regimenz	XXX	XXX	XXX	XXX	XXX
	...	XXX	XXX	XXX	XXX	XXX
Line 2	Regimenx	XXX	XXX	XXX	XXX	XXX
	Regimeny	XXX	XXX	XXX	XXX	XXX
	Regimenz	XXX	XXX	XXX	XXX	XXX
	...	XXX	XXX	XXX	XXX	XXX
Line 3	Regimenx	XXX	XXX	XXX	XXX	XXX
	Regimeny	XXX	XXX	XXX	XXX	XXX
	Regimenz	XXX	XXX	XXX	XXX	XXX
	...	XXX	XXX	XXX	XXX	XXX

Lines of therapy are progression-based and are restricted to the first 3 lines.

Table 3b. Summary of Treatment Regimen Duration – Palbociclib + AI Patients

Repeat Table 3a for patients receiving Palbociclib with AI as initial endocrine-based therapy.

[figure not shown]
CCI

Table 4a. Summary of Treatment Sequencing Duration – All Eligible Patients

	Treatment Sequence	Duration (month)				
		n	%	Mean	SD	Median
One line	Line 1 Regimenx	XXX	XXX	XXX	XXX	XXX
	Line 1 Regimeny	XXX	XXX	XXX	XXX	XXX
	Line 1 Regimenz	XXX	XXX	XXX	XXX	XXX
	...	XXX	XXX	XXX	XXX	XXX
Two lines	Line 1 Regimen ==> Line 2 Regimen	XXX	XXX	XXX	XXX	XXX
	Line 1 Regimen ==> Line 2 Regimen	XXX	XXX	XXX	XXX	XXX
	Line 1 Regimen ==> Line 2 Regimen	XXX	XXX	XXX	XXX	XXX
	...	XXX	XXX	XXX	XXX	XXX

PFIZER CONFIDENTIAL

Three lines	Line 1 Regimen ==> Line 2 Regimen ==> Line 3 Regimen	xxx	xxx	xxx	xxx	xxx
	Line 1 Regimen ==> Line 2 Regimen ==> Line 3 Regimen	xxx	xxx	xxx	xxx	xxx
	Line 1 Regimen ==> Line 2 Regimen ==> Line 3 Regimen	xxx	xxx	xxx	xxx	xxx
	...	xxx	xxx	xxx	xxx	xxx

Lines of therapy are progression-based and are restricted to the first 3 lines.

Table 4b. Summary of Treatment Sequencing Duration – Palbociclib + AI Patients

Repeat Table 4a for patients receiving Palbociclib with AI as initial endocrine-based therapy.

CCI

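### SAP 5.2 defines Treatment Sequence Duration within one line of therapy, so it supplies no value for the two-line and three-line rows of Tables 4a and 4b

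*SAP*

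**What the plan says.** **Definition.** SAP 5.2 defines Treatment Sequence Duration as the time in months from the start of the first regimen "to the end date of the last treatment regimen within the same line of therapy". It uses the data cutoff as the end date of an ongoing regimen and adds: "This will be calculated for up to 3 lines of therapy".

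**Output.** The shell for this endpoint is "Table 4a. Summary of Treatment Sequencing Duration – All Eligible Patients" in SAP Appendix 1, which Table 4b repeats for the palbociclib + AI cohort. The shell has three blocks, for one, two and three lines. Rows in the second block read "Line 1 Regimen ==> Line 2 Regimen" and rows in the third read "Line 1 Regimen ==> Line 2 Regimen ==> Line 3 Regimen". Each row has one n, %, mean, SD and median. The footnote says only that lines are progression-based and limited to the first three.

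**Lines.** SAP 5.3 takes over the protocol's progression-based lines, "in which a disease progression must occur for a new regimen to be interpreted as a new line of therapy".

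**Objective.** Objective 1b (Protocol section 8, repeated in SAP 2.2) includes "Sequence of regimens across lines, through the end of the record of systemic therapy".

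**The concern.** The definition stops the clock inside one line, while most of the table describes sequences that cross lines. The rule and the output cannot both hold for the two-line and three-line rows.

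Treatment Sequence Duration is a named treatment-pattern endpoint, and Table 4 serves a primary objective. With the text as it stands, whoever programs the table must choose what to put in the multi-line rows, and the SAP does not say which choice is right. Readers will naturally take the figure beside a two-line or three-line sequence as time on the whole sequence. If it is something else, nothing in the table will tell them.

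**Working it through.** The documents give no figure to reproduce, because Table 4a is an empty shell. The check is a comparison of texts, followed by simple algebra.

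1. **Can a multi-line row lie within one line?** No. SAP 5.3 requires a progression before a new line starts. Line 1 and Line 2 are therefore always different lines.

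2. **What does the written rule produce?** Let L1, L2 and L3 be the within-line durations, each from the start of the first regimen to the end of the last regimen of that line. Let g12 and g23 be the gaps between lines. Protocol 9.3.1 says that a progression ends a regimen and that treatment continued afterwards counts as a new regimen. Lines therefore do not overlap, and g12 and g23 are zero or positive.
   - One-line row: the rule gives L1, which is the duration of the sequence. The row is sound.
   - Two-line row: the rule gives L1 and L2, two values for one entry.
   - Three-line row: the rule gives L1, L2 and L3, three values for one entry.

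3. **What would the row label lead a reader to expect?**
   - Two lines: L1 + g12 + L2 (full span), or L1 + L2 if gaps are left out.
   - Three lines: L1 + g12 + L2 + g23 + L3, or L1 + L2 + L3 without gaps.

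   None of these is a within-line duration.

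4. **Direction of any error.** If L1 were entered in a two-line row, it would fall short of the span by g12 + L2. If L2 were entered, it would fall short by L1 + g12. Both amounts are positive, and the same holds for any single line in a three-line row. The direction is certain. The size depends on line lengths and gaps that the documents do not give.

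5. **Does other text settle it?**
   - The sentence on up to three lines most naturally means that the within-line calculation is repeated for each line. That again gives several values per row.
   - The Table 4a footnote limits the number of lines and gives no duration rule.
   - Duration of all treatment (SAP 5.3, Figures 4a and 4b) does cross lines. It is a separate Kaplan-Meier endpoint that runs to the end of the last line with no three-line limit, and nothing links it to Table 4.
   - Protocol 9.3.1 leaves the details of subsequent lines to the SAP, so the protocol does not fill the gap.
   - No redaction falls on the definition or on the Table 4a rows.

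**The case against.** **The intention may be clear enough.** The sentence on up to three lines, read beside blocks for one, two and three lines, could mean a sequence running through up to three lines. That matches the shell and may be what the authors meant. It does not fit the explicit restriction to the same line, so the text still needs correcting.

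**A reader might infer that the rule produces a definite wrong number, or that a programmer would enter single-line times.** The documents support neither. No unique number follows from the rule, and the row labels make the mismatch visible enough that a query is at least as likely.

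**A reader might try to put a percentage on the error.** Taking the 24.5-month median PFS in Protocol section 7 as Line 1, and assuming a Line 2 of 6 to 12 months with no gap, gives 24.5/30.5 = 0.80 and 24.5/36.5 = 0.67. Entering Line 1 alone would then be 20% to 33% short. This is arithmetic and not an estimate for this study. The 24.5 months is an all-patient PFS median from another dataset. Patients in a two-line row have by definition progressed and started a second line within limited follow-up, which Protocol 9.5 puts at 33 months on average. Their Line 1 time may be quite different, and the Line 2 range is an assumption.

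**A reader might infer that Objective 1b requires a cross-line duration.** It asks for the sequence across lines, which the n and % columns answer. The need for a matching duration comes from the Table 4 shell, not from the objective.

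**Related times are reported elsewhere.** Table 3a gives regimen durations for Lines 1 to 3, and Duration of all treatment gives a total. This limits the loss, but neither gives duration by sequence.

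**The study is descriptive.** SAP 3.1 and 3.2 state no hypotheses or decision rules, so no inference is affected. That is correct and keeps the point modest.

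**Conclusion.** The inconsistency is real and can be read directly from SAP 5.2 and Table 4a. For the two-line and three-line rows of Tables 4a and 4b, and of any further table that repeats Table 4a, the written rule gives two or three within-line values and none that fits the row.

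The reach is limited to the duration statistics in those rows. The size of any error cannot be derived from the documents. The conclusion that a single-line entry would be too short rests only on lines not overlapping and each line having positive length. The point should be settled before Table 4 is programmed.

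**What to change.** **Preferred.** In SAP 5.2, define the duration reported in Table 4 as months from the start of the first regimen in Line 1 to the end of the last regimen in the last line shown in that row, with the data cutoff as the end date if that regimen is ongoing. State also that:

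- gaps between lines are included;
- patients with more than three lines enter the three-line rows, with the clock stopped at the end of Line 3.

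**Alternative.** Keep the within-line definition and replace the single duration block in Table 4 with separate, labelled columns for Line 1, Line 2 and Line 3.

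The first option costs a few sentences in SAP 5.2. The second costs extra columns in the Table 4 shells. Either can be derived from the regimen and line dates already planned, so no new data are needed.
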